8.1 Statistical considerations

• Analyses will be performed by AstraZeneca or its representatives.

A comprehensive Statistical Analysis Plan (SAP) will be prepared prior to first patient enrolled and any subsequent amendments will be documented.

8.2 Sample size estimate

The primary objective of the trial is to describe the safety profile of osimertinib in routine clinical practice and add to the limited burden of safety data on osimertinib currently available as assessed by the incidence of adverse events (AEs) (Serious and Non-serious AEs) observed during trial. Considering the epidemiology of metastatic NSCLC-adenocarcinoma subtype which are positive for EGFR sensitizing mutation and have progressed after EGFR-TKI based treatment in first line setting and prevalence of T790M-mutation after such progression, a sample size of 60 patients is expected to provide the following exact two sided 95% confidence interval for a list of percentages of patients reporting at least one AE (Julious and Campbell 2012).

Observed rate expressed as % (number of patients reporting at least one AE*)	Lower Limit of CI (%)	Upper Limit of CI (%)
0%	0	6.0
1%	0	7.8
2%	0.1	9.5
5%	1.0	13.9
10%	3.8	20.5
20%	10.8	32.3
30%	18.8	43.2
40%	27.6	53.5
50%	36.8	63.2

^{*}the symptom could be any of the expected AE, unexpected AE or SAE. The calculation is based on the link between binomial and beta distributions.

8.3 Description of outcome variables in relation to objectives

Analysis will be conducted to evaluate the following as available in the CRF:

- Baseline characteristics: demographics, relevant medical history, disease characteristics, cancer treatment history.
- Exposure to the study drug
- Adverse events SAEs, AEs leading to dose modification or discontinuation, and AEs of special interest (for example interstitial lung disease/pneumonitis-like events; QTc prolongation events)
- Death due to AE, or unknown cause (except death due to disease progression).

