The USA-based National Comprehensive Cancer Network (NCCN) guidelines included osimertinib as one of the recommended treatment options following first-line therapy with erlotinib, afatinib or gefitinib ("NCCN Clinical Practice Guidelines in Oncology (NCCN Guidelines®)- Non-Small Cell Lung Cancer (Version 8.2017)" 2017).

51st patient expert committee (SEC) of oncology and hematology on 21-Mar-2017 has given positive recommendations for approval of osimertinib for "the treatment of patients with metastatic epidermal growth factor receptor (EGFR) T790M mutation-positive nonsmall cell lung cancer (NSCLC), as detected by an appropriate test, who have progressed on or after EGFR TKI therapy" with a condition to conduct phase IV clinical trial as per the requirements of Indian Good Clinical Practices (GCP) and schedule Y of Drugs and Cosmetics Rules, 1945.

As per recommendation, current phase-IV study is planned with the aim to assess the safety of osimertinib in Indian patients as a post-marketing requirement. The data obtained from the present study will help to understand the safety profile of osimertinib in Indian patients with EGFR-T790M mutation-positive NSCLC and add to the limited burden of safety data on osimertinib currently available.

OBJECTIVES

Primary Objective:	Primary Outcome Measure:
	Number, frequency and proportion of patients with adverse events (AEs), serious adverse events (SAEs) and AEs of special interest (AESI) including interstitial lung disease/pneumonitis-like events, and on-study deaths.

STUDY DESIGN

This is a prospective, single-arm, multicenter, phase-IV trial investigating the safety of osimertinib in Indian adult patients with locally advanced or metastatic EGFR-T790M mutation-positive NSCLC. Investigator will be trained on the locally approved prescribing information before the enrolment of the first patient at their site to ensure compliant and proper dosing of the study drug. Patients will be monitored throughout the study period for AEs of osimertinib.

The decision of patients to participate in this study must not, in any way, impact upon the standard of care that they are receiving or any benefits to which they are otherwise entitled. Prior to data collection, all patients must sign an informed consent form (ICF) allowing data collection and source data verification in accordance with local requirements and sponsor policy.

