The Treatment Phase will extend from Cycle 1, Day 1 to Cycle 6, Day 21; or until study drug discontinuation due to either disease progression or unacceptable toxicity; or other reasons whichever occurs first, as listed in Section 3.9. Patients may continue to receive osimertinib as long as they are continuing to show clinical benefit, as judged by the investigator, and in the absence of discontinuation criteria.

POST STUDY ACCESS TO STUDY TREATMENT

Patients receiving osimertinib at the time of study completion (i.e. after completion of treatment phase) may continue to receive osimertinib, if in the opinion of their treating physician they are continuing to derive clinical benefit from continued treatment or have not progressed clinically. They will be provided osimertinib treatment as per recommendation from treating physician on ethical basis. Post-trial access to osimertinib will be provided from local commercial supply though local distribution channel. Such patients will not be monitored after EOS visit.

STUDY DRUG, DOSAGE AND MODE OF ADMINISTRATION

Osimertinib is an oral, potent, selective, irreversible inhibitor of both EGFR-TKI sensitizing and resistance mutations in NSCLC with a significant selectivity margin over wild-type EGFR. osimertinib will be administered orally as one 80 mg tablet once a day. A cycle of treatment is defined as 21 days of once daily osimertinib treatment. Dose modification will be done as per locally approved prescribing information with the use of 40 mg tablet strength if required.

SAFETY EVALUATIONS

Safety evaluations will include adverse event monitoring, physical examinations, ECG monitoring, clinical laboratory parameters (hematology and biochemistry), vital sign measurements, and WHO performance status and death as observed by the investigator. Based on the previous human experience with osimertinib, in vitro studies, and animal toxicological findings, interstitial lung disease (ILD), QT_c interval prolongation, cardiomyopathy and keratitis will be closely monitored. Any of the safety monitoring assessments may be performed more frequently, and adverse events should be evaluated by the investigator according to the standard practice if clinically indicated.

Statistical methods

SAMPLE SIZE JUSTIFICATION

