1.4 Study Design

This is a prospective, single-arm, multicenter, phase-IV trial investigating the safety of osimertinib in Indian adult patients with metastatic EGFR-T790M mutation-positive NSCLC. Investigator will be trained on the locally approved prescribing information before the enrolment of the first patient at their site to ensure compliant and proper dosing of the study drug. Patients will be monitored throughout the study period for AEs of osimertinib.

2. Study Objectives

Primary Objective:	Primary Outcome Measure:
To assess the safety of osimertinib among T790M positive NSCLC patients of India	• Number, frequency and proportion of patients with adverse events (AEs), serious adverse events (SAEs) and AEs of special interest (AESI) including interstitial lung disease/pneumonitis-like events, and on-study deaths.

3. Patient Selection, Enrolment, Randomisation, Restrictions, Discontinuation and Withdrawal

Each patient should meet all of the inclusion criteria and none of the exclusion criteria for this study. Under no circumstances can there be exceptions to this rule.

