6.3.7 Disease progression

Disease progression can be considered as a worsening of a patient's condition attributable to the disease for which the investigational product is being studied. It may be an increase in the severity of the disease under study and/or increases in the symptoms of the disease. The development of new, or progression of existing metastasis to the primary cancer under study should be considered as disease progression and not an AE. Events that are unequivocally due to disease progression should not be reported as AEs during the study.

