8.5.1 Analysis of the primary variable (s)

Adverse Events

The verbatim terms used in the CRF by investigators to identify adverse events will be coded using the Medical Dictionary for Regulatory Activities (MedDRA) and CTCAE grade and will be listed individually by patient. Treatment-emergent adverse events are adverse events with onset during the treatment phase or that are a consequence of a pre-existing condition that has worsened since baseline. All reported adverse events will be included in the analysis. For each adverse event, the percentage of subjects who experience at least 1 occurrence of the given event will be summarized.

Any AE occurring before treatment with osimertinib will be included in the data listings but will not be included in the summary tables of AEs. Any AE occurring within 28 days of discontinuation of investigational product (ie, the last dose of osimertinib) will be included in the AE summaries.

Any events in this period that occur after a patient has received further therapy for cancer (following discontinuation of osimertinib) will be flagged in the data listings.

Adverse events of special interest (for example interstitial lung disease/pneumonitis-like events; QTc prolongation events]) will be summarized separately.

Summaries, listings, datasets, or subject narratives may be provided, as appropriate, for those subjects who die, who discontinue treatment due to an adverse event, or who experience a severe or a serious adverse event.

Clinical Laboratory Tests

Laboratory data will be summarized by type of laboratory test. Descriptive statistics will be calculated for each laboratory analyte at baseline and for observed values and changes from baseline at each scheduled time point. Changes from baseline results will be presented in pre- versus posttreatment cross-tabulations (with classes for below, within, and above normal ranges). Parameters with predefined National Cancer Institute Common Terminology Criteria for Adverse Events (NCI-CTCAE) toxicity grades will be summarized. Change from baseline to the worst adverse event grade experienced by the subject during the study will be provided as shift tables. A listing of subjects with any laboratory results outside the reference ranges will be provided. A listing of subjects with any markedly abnormal laboratory results will also be provided.

Electrocardiogram (ECG)

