## 8. Statistical Analysis

### 8.1 Patient Disposition

A tabular presentation of the patient disposition will be provided. It will include the number of patients screened, enrolled/ assigned treatment, completed, as well as the number of dropouts, with reasons for discontinuation. All patients entered in the study will be accounted for in this. A listing will be presented to describe dates of screened,

assigned treatment, screen failed with reason, completion, early withdrawal, and the reason for early discontinuation, if applicable, for each patient.

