## 8.7 Safety Analysis

### 8.7.1 Adverse Events

All adverse events (AEs) will be coded by System Organ Class (SOC) and Preferred Term (PT) according to the Medical Dictionary for Regulatory Activities (MedDRA) Version 23.0. The intensity of adverse events is graded by the National Cancer Institute (NCI) Common Terminology Criteria for Adverse Events (CTCAE) version 4.0 or higher.

*Treatment-emergent adverse events are adverse events with onset during the treatment phase or that are a consequence of a pre-existing condition that has worsened since baseline. All reported adverse events will be*

*included in the analysis. For each adverse event, the percentage of subjects who experience at least 1 occurrence of the given event will be summarized.*

*Any AE occurring before treatment with osimertinib will be included in the data listings but will not be included in the summary tables of AEs. Any AE occurring within 28 days of discontinuation of investigational product (i.e., the last dose of osimertinib) will be included in the AE summaries.*

*Any events in this period that occur after a patient has received further therapy for cancer (following discontinuation of osimertinib) will be flagged in the data listings.*

*Adverse events of special interest (for example interstitial lung disease/pneumonitis-like events; QTc prolongation events) will be summarized separately.*

*Summaries, listings, datasets, or subject narratives may be provided, as appropriate, for those subjects who die, who discontinue treatment due to an adverse event, or who experience a severe or a serious adverse event.*

An overall summary will be provided in terms of count and percentages for:

- AEs
- TEAEs
- Grade 3 and above TEAEs
- Grade 3 and above related TEAEs
- Treatment-related TEAEs
- Treatment-related serious TEAEs
- TEAEs leading to dose change/ interruption/ discontinuation
- Treatment related TEAEs leading to dose change/ interruption/ discontinuation
- Serious TEAEs
- Fatal TEAEs
- Related Fatal TEAEs

Summaries in terms of count and percentages by SOC and PT will be provided for the following:

- TEAEs
- Treatment-Emergent SAEs
- Grade 3 and above TEAEs
- Treatment-related TEAEs
- Grade 3 and above treatment-related TEAEs
- TEAEs leading to dose change/ interruption/ discontinuation
- Adverse Events of special interest

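### The primary outcome counts on-study deaths without a cause limit, but protocol 8.3 drops progression deaths and no committed SAP output gives the proportion of all on-study deaths

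*Protocol*

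**What the plan says.** Protocol section 2 defines the primary outcome as counts and proportions of patients with AEs, SAEs and "AEs of special interest (AESI) including interstitial lung disease/pneumonitis-like events, and on-study deaths". The synopsis uses the same wording. Neither limits the cause of death. The synopsis also lists "WHO performance status and death as observed by the investigator" among the safety evaluations, as an item apart from adverse event monitoring.

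Protocol 8.3, whose heading ties the outcome variables to the objectives, gives the death variable as "Death due to AE, or unknown cause (except death due to disease progression".

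Protocol 6.3.7 adds a reporting rule: "Events that are unequivocally due to disease progression should not be reported as AEs during the study".

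SAP 8.7.1 commits to counts and percentages of fatal TEAEs and "Related Fatal TEAEs". It also repeats a sentence from protocol 8.5.1: "Summaries, listings, datasets, or subject narratives may be provided, as appropriate, for those subjects who die". SAP 8.1 commits to a disposition table with the number "completed, as well as the number of dropouts, with reasons for discontinuation".

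**The concern.** Safety is the only objective of this trial, and death is one of the named components of its primary outcome. That component has one scope in section 2 and a narrower one in 8.3, and neither section 2 nor the synopsis points to 8.3. The SAP does not settle the matter: its section 2 restates the objective but not the outcome measure, and its death rows are built on AE reports.

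Two things are at stake. The reported death figure may be smaller than the one the primary outcome promises. The count also comes to depend partly on the investigator's judgement that a death was due to progression, in an open-label trial with no comparator. The word unequivocally in 6.3.7 limits that dependence but does not remove it. A count of deaths from any cause would not have it at all.

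**Working it through.** **1. The plan's own figure.** Inputs: n = 60 and an exact two-sided 95% interval (protocol 8.2, SAP 4). With x = rate × 60, the lower limit is the 2.5% quantile of Beta(x, n − x + 1) and the upper limit is the 97.5% quantile of Beta(x + 1, n − x).

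- 5%: x = 3 gives 1.04 to 13.92 (stated 1.0 to 13.9).
- 10%: x = 6 gives 3.76 to 20.51 (stated 3.8 to 20.5).
- 20%: x = 12 gives 10.78 to 32.33 (stated 10.8 to 32.3).

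All nine rows reproduce to within 0.05 percentage point. The table contains no death rate, so the point rests on the text and not on these figures.

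**2. The places that deal with death, side by side.**

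| Place | Deaths covered | Firm output? |
|---|---|---|
| Protocol synopsis and section 2 | All on-study deaths, no cause limit | Primary outcome |
| Protocol 8.3 | AE or unknown cause; progression excluded | Analysis variable |
| SAP 8.7.1, two fatal TEAE rows | Deaths reported as AEs | Yes |
| Protocol 8.5.1 and SAP 8.7.1, subjects who die | No cause limit | No, optional wording |
| SAP 8.1 disposition | Death possible as a reason, not named | Table yes, death row no |

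**3. Count of SAP outputs specific to death.** 2 of the 11 overall AE rows and 0 of the 7 SOC/PT summaries in SAP 8.7.1; 0 of the 15 listings in SAP 8.7.5. The SOC/PT summary of treatment-emergent SAEs would include fatal AEs, but it does not recover deaths that were never reported as AEs.

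**4. One death traced through the plan.** Take a patient who stops drug for progression, enters follow-up and dies, unequivocally of progression, within 28 days of the last dose.

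- Section 2 counts this death; 8.3 excludes it.
- Under 6.3.7 the event is not an AE, so it cannot enter either fatal TEAE row.
- In SAP 8.1 the patient appears under death if the reasons are for leaving the study (protocol 3.10.1 lists death), or under progression if they are for stopping treatment (protocol 3.9 lists progression).
- A patient who finished six cycles and died in follow-up could be shown as a completer.

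**5. Size per death.** If all 60 planned patients are in the safety set, each omitted death lowers the reported proportion by 1/60 = 1.67 percentage points.

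**6. Illustration.** The death counts below are assumptions, not figures from the documents (n = 60, exact 95% intervals).

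| All deaths | % (95% CI) | Not due to progression | % (95% CI) |
|---|---|---|---|
| 3 | 5.0 (1.0 to 13.9) | 1 | 1.7 (0.04 to 8.9) |
| 6 | 10.0 (3.8 to 20.5) | 2 | 3.3 (0.4 to 11.5) |
| 12 | 20.0 (10.8 to 32.3) | 3 | 5.0 (1.0 to 13.9) |

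These show only that the two definitions can give different results.

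**The case against.** The best reply is that SAP 8.1 already covers all deaths. The table is mandatory, accounts for every patient entered and comes with a per-patient listing. Death is a study-withdrawal reason in protocol 3.10.1 with no cause limit. Progression is not on that list, and under 3.9 stopping drug does not by itself withdraw a patient. Read at study level, a patient who progresses and then dies in follow-up would leave as a death. SAP 5.1 and 5.4 would then supply a percentage in the safety set.

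This reading is plausible, but SAP 8.1 does not state it. The section names no death row and no level of discontinuation, so the proportion depends on how a programmer interprets it.

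A second reply is that 8.3 exists to specify section 2, and that leaving out progression deaths is coherent for a drug-safety objective. That is a fair reading: section 2 does not say any cause, and the synopsis item on death is only indirect support for it. Even so, the SAP would have no output matching 8.3, because deaths of unknown cause appear only if they were reported as fatal TEAEs. An edit is needed on either reading.

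Three further points stand. The size is not established, no test or decision rule depends on it (SAP 7.1), and the attribution risk is limited, because equivocal deaths stay reportable and 8.3 keeps unknown-cause deaths.

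**Conclusion.** The concern holds. Section 2 and 8.3 disagree on which deaths count, and no committed output gives the proportion of all on-study deaths. The disposition table may show some or all of them, but the SAP does not commit it to do so.

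The size is 1.7 percentage points per omitted death, assuming a safety set of 60. The total effect is unknown, because the documents give neither a death rate nor a split by cause. The conclusion takes on-study deaths to mean deaths from any cause, which is the most natural reading though not an explicit one.

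This should be fixed, since it concerns a named component of the primary outcome. It does not undermine the rest of this descriptive analysis.

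**What to change.** - **SAP 8.7.1:** define on-study death as death from any cause between the first dose and 28 days after the last study dose. Report n and % in the safety set by investigator-assigned cause (AE, progression, other, unknown), and keep fatal TEAEs as a subset.
- **Protocol 8.3:** present non-progression deaths as a subset of all on-study deaths, so that it agrees with section 2.
- **SAP 8.1:** state whether the reasons are for stopping treatment or for leaving the study.
- **Check, not a defect:** confirm that the CRF, which is not among the documents, records date and cause for every death. Protocol 6.3.3 lists these among the variables collected for SAEs.

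The cost is one extra table, one line in protocol 8.3 and one clarification in SAP 8.1. No planned output is lost. If the protocol can no longer be amended, the SAP definition and table still correct the reporting. The reported death figure may be higher.

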8.4 Definitions of analysis sets

8.4.1 Safety analysis set

Safety analysis set will include all enrolled patients who received at least one dose of study medication during treatment period.

8.5 Methods for statistical analyses

Data will be summarized using descriptive statistics. Continuous variables will be summarized using the number of observations, mean, SD, coefficient of variation, median, and range as appropriate. Categorical values will be summarized using the number of observations and percentages as appropriate. Shift tables will be provided to determine the change in reported outcomes from baseline.

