Visit No.	1	2-7 (Day 1 of each cycle)	8	202
Study Days	-6 to 0	1-109 (21 day per cycle)	131	28 days post- EOT
Screening/Enrolment visit				
Informed consent ^(b)	Patients r	nust sign the informed conser procedures are p		study-specific
Eligibility Criteria	X			
Demographics/ Review medical history	X			
WHO Performance Status	X	X	X	
General Physical examination	X	Symptom-directed physical	examination only	
Concomitant medication recording	Continuous from time of ICF until 28 days after last osimertinib dose in treatment phase.			
Study Drug Administration				
Osimertinib dosing		The recommended dose is 80 mg osimertinib once a day until disease progression or unacceptable toxicity. Each cycle is of 21 days.		
Disease Evaluations (Disease char	racteristics wil	ll be performed as per routine	clinical practice)	
Baseline Disease Characteristics	X			
Safety Evaluations				
Physical examination	X	Symptom-directed physical examination only		
Vital parameters	X	X	X	
Adverse event monitoring		us from time of ICF until 28 days after last study osimertinib dose		
12-lead ECG	X	X	X	
Hematology & Biochemistry	X	X	X	

Footnotes:

- a. The Screening Phase begins when the first Screening procedure is conducted. Screening tests should be performed within 7 days of Cycle 1 Day 1 except for disease evaluations (performed as routine clinical practice).
- b. Must be signed before first study-related activity.

TABLE OF CONTENTS

PAGE

TITLE	PAGE	1
VERSIO	ON HISTORY	2
PROTO	COL SYNOPSIS	3
TIME A	AND EVENTS SCHEDULE	8
TABLE	OF CONTENTS	9
1.	Introduction	13
1.1	Background and rationale for conducting this study	13
1.2	Rationale for study design, doses and control groups	14
1.3	Benefit/risk and ethical assessment	14
1.4	Study Design	14
2.	Study Objectives	14
3.	Patient Selection, Enrolment, Randomisation, Restrictions, Discontinuation and Withdrawal	15
3.1	Inclusion criteria	15
3.2	Exclusion criteria	15
3.3	Patient enrolment and randomization	15
3.4	Procedures for handling incorrectly enrolled or patients	16
3.5	Methods for assigning treatment groups	16
3.6	Methods for ensuring blinding	16
3.7	Methods for unblinding	16
3.8	Restrictions	16
3.9 3.9.1	Discontinuation from study treatment Procedures for discontinuation of a patient from study drug	
3.10 3.10.1	Criteria for withdrawal	
3.11	Discontinuation of the study	18
4.	Study Plan and Timing of Procedures	19
5.	Study Assessments	20
5.1 5.1.1 5.1.2 5.1.3	Safety assessments Laboratory safety assessments Physical examination	21

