## 7. Method of Analysis

### 7.1 Statistical Hypotheses

*No formal hypothesis testing will be conducted.*

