**Clinical Chemistry (serum or plasma)**

Creatinine

Bilirubin, total

Leukocyte differential count (absolute count)	Alkaline phosphatase (ALP)
Platelet count	Aspartate transaminase (AST)
	Alanine transaminase (ALT)
	Albumin
	Potassium
	Calcium, total
	Sodium
	Creatine kinase (CK)

*Changes from baseline results will be presented in pre- versus post treatment cross-tabulations (with classes for below, within, and above normal ranges). Parameters with predefined National Cancer Institute Common Terminology Criteria for Adverse Events (NCI-CTCAE) toxicity grades will be summarized. Change from baseline to the worst adverse event grade experienced by the subject during the study will be provided as shift tables.*

Lab toxicity grades will be derived using NCI-CTCAE version 5.0.

*A listing of subjects with any laboratory results outside the reference ranges will be provided. A listing of subjects with any markedly abnormal laboratory results will also be provided.*

*Physical Examinations*

*A listing of physical examinations will be provided.*

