#### 8.7.5 *Other Safety Parameters*

WHO performance status will be summarized with number and percentage for each status per cycle.

A listing will be provided for each of the following:

- WHO performance status
- Pathology at Diagnosis
- Tumour sample
- Extent of disease
- Previous cancer therapy
- Previous radiotherapy
- Receptor status
- Pregnancy test
- Ejection fraction measurements
- Skin Reaction
- Pregnancy report
- Drug administration
- Drug accountability
- Drug Overdose
- Hospital admission details

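### SAP 5.1 promises shift tables from baseline, but SAP 8.7.5 specifies only a per-cycle distribution for WHO performance status, so no specified table shows how many patients worsened

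*Protocol*

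**What the plan says.** Protocol 8.5 sets a general rule: "Shift tables will be provided to determine the change in reported outcomes from baseline". SAP 5.1 carries the same sentence. Neither document says which outcomes the rule covers.

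The protocol synopsis lists the safety evaluations, including "vital sign measurements, and WHO performance status and death as observed by the investigator". The Time and Event Schedule (protocol Table 1) marks "WHO Performance Status" at screening, on Day 1 of each of Cycles 1 to 6, and at EOT.

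SAP 8.7.5 (numbering of the SAP body) then specifies the analysis: "WHO performance status will be summarized with number and percentage for each status per cycle". Below that comes "A listing will be provided for each of the following", with WHO performance status as the first item.

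Other safety variables are handled differently. For laboratory grades SAP 8.7.2 says "Change from baseline to the worst adverse event grade experienced by the subject during the study will be provided as shift tables", and it adds pre- versus post-treatment cross-tabulations by normal range. Vital signs (SAP 8.7.3) and QTc (SAP 8.7.4) get change from baseline. Laboratory tests, vital signs and ECG each have a written baseline definition. WHO performance status has none.

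**The concern.** A percentage in each status at each cycle describes the group present at that cycle. It does not connect a patient to his or her own starting value. One patient moving from 0 to 1 and another moving from 1 to 0 leave the table unchanged. A flat series of percentages could therefore be read as performance status being maintained when some patients had declined.

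The adverse event tables only partly cover this. Under protocol 6.3.6, deterioration from baseline in mandated laboratory tests, vital signs and other safety assessments is reported as an adverse event only if it meets a seriousness criterion or is the reason for stopping the drug; the stated reason is that these results will be summarised in the study report. On a natural reading that includes performance status. Protocol 6.3.7 also keeps events unequivocally due to progression out of adverse event reporting. Decline in performance status as such therefore depends largely on its own summary.

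The baseline gap has a practical side. Status is scheduled at both screening and Cycle 1 Day 1, and the SAP does not say which value is the reference.

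**Working it through.** **The plan's own figure.** The plan gives no number for performance status. Its one statistical figure is the table for which "a sample size of 60 patients is expected to provide the following exact two sided 95% confidence interval". Clopper-Pearson limits with n = 60 reproduce all nine rows to one decimal (for example 5%: 1.04 to 13.92; 50%: 36.81 to 63.19). Nothing below depends on that table.

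**What each SAP section specifies**

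| Variable | Baseline defined | Within-patient change shown in a table |
|---|---|---|
| Laboratory (8.7.2) | yes | yes: change, cross-tabulation, baseline-to-worst shift |
| Vital signs (8.7.3) | yes | yes: change from baseline |
| QTc (8.7.4) | yes | yes: change from baseline, maximum increase |
| WHO performance status (8.7.5) | no | no: distribution per cycle only |

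**What two distributions can tell the reader.** The documents give no performance status distribution, so the counts here are assumed. All 60 patients are taken as assessed at both times.

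- Two levels, 30 at status 0 and 30 at status 1, both times. Let w be the number moving from 0 to 1. The later count at status 0 is 30 − w + (number moving from 1 to 0). For this to equal 30, the number improving must also be w. Any w from 0 to 30 is possible, so the number worsened is 0 to 30 of 60 (0% to 50%).
- Three levels (0/1/2), baseline 20/30/10. In these examples the maximum is reached when all 20 patients at status 0 worsen and every later status 2 place is filled by a patient from status 1. The minimum is the smallest number of worsening moves that the two distributions force.

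| Later distribution | Minimum worsened | Maximum worsened |
|---|---|---|
| 20/30/10 | 0 | 20 + 10 = 30 |
| 15/30/15 | 5 | 20 + 15 = 35 |
| 25/28/7 | 0 | 20 + 7 = 27 |

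**The shrinking group.** Cycle 6 Day 1 is day 5 × 21 + 1 = 106. The protocol background quotes a median progression-free survival of 10.1 months on osimertinib. Assume exponential event times and 30.44 days per month:

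1 − 0.5^((106/30.44)/10.1) = 1 − 0.5^0.345 = 21.3%, and 0.213 × 60 = 12.8, about 13 patients.

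This treats every progression-free survival event as a departure. It describes the denominator only and does not measure how many patients worsen.

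A worked case, again assumed: start from 30 at status 0 and 30 at status 1. Thirteen of the status 1 patients decline and leave, and nobody else changes. The share at status 0 moves from 30/60 = 50% to 30/47 = 64%. The cycle table shows apparent improvement although 13 patients worsened and none improved. Those declines may be recorded at EOT, a visit that SAP 8.7.5 does not name.

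**The case against.** The strongest reply is that nothing has been breached. SAP 5.1 repeats the protocol's shift-table sentence, and SAP 8.7.5 does not say that the per-cycle table is the only one. If 5.1 covers performance status, a shift table is already planned; if it does not, no promise about performance status was made. Protocol 8.3 does not list performance status among the outcome variables, protocol 8.5.1 gives no method for it, and the only variable to which the protocol attaches a shift table is laboratory grades. This stands as far as it goes. A reader might infer that the SAP dropped something the protocol required, and the documents do not support that. What remains is that the SAP's general statement and its specific instruction lead to different outputs, and a programmer working from 8.7.5 would produce no shift table.

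The listing is a fair second reply. With about 60 patients and at most eight scheduled assessments each, worsening can be counted from it. But such a count has no baseline definition and no rule for choosing the later value, so it is not a prespecified result.

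Third, the stakes are low. Performance status is not in the primary outcome measure, the SAP states "No formal hypothesis testing will be conducted", and symptoms that accompany a decline can still be recorded as adverse events. All of this is correct and limits the weight of the point.

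Finally, baseline-to-worst is one format among several. It counts a single transient reading as worsening, and in a single-arm study it cannot separate drug effect from disease. That argues for labelling the table as descriptive, and leaves the need for a within-patient summary intact.

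**Conclusion.** The point holds as an internal inconsistency in the SAP. The only table specified for WHO performance status cannot yield the number of patients who worsened, although paired values are scheduled and the SAP's general section calls for shift tables.

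Its size cannot be stated from the documents. The range of 0 to 30 of 60 is a mathematical limit on an assumed 30/30 split; its upper end needs every status 0 patient to worsen and every status 1 patient to improve. A reader might take it as a likely error in the report, and it is not one. The 21.3% figure rests on an exponential assumption and shows only that the later cycle tables may describe a smaller and different group.

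The matter is minor and supportive. No sample size, confidence interval or primary result changes.

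**What to change.** In SAP 8.7.5:

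- Define baseline WHO performance status as the last value before first dose.
- Add one shift table of baseline status against worst status after first dose, including the EOT value and a missing category.
- Report n (%) worsened by 1 or more levels and by 2 or more levels, among safety-set patients with a baseline and at least one later value.
- Keep the per-cycle table as support, with the number assessed at each cycle.

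In SAP 5.1, name the outcomes that get shift tables, so that the general sentence and the variable-specific sections agree.

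The cost is a SAP wording change and one table from data already scheduled for collection. It needs no new assessments, no change in sample size and no protocol amendment.
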